Study Period	Description
Stage I	Day 1 to [REDACTED] trial intervention administration and safety/efficacy assessments
Stage II	Post [REDACTED] trial intervention administration and safety/efficacy assessments + safety follow-up

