4.4.4 Stage II Analysis Set

The stage II analysis set includes all participants who received at least one dose of trial intervention during the Stage II treatment period starting from [REDACTED].

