4.9 Safety Analyses

4.9.1 Adverse Events

Safety analyses will be based on the actual treatment received and will be performed on the Safety Analysis Set, Stage II Analysis Set or Any Daxdilimab Set according to the study period being examined. All safety data will be provided in patient listings by treatment group.

No formal hypothesis is planned. In general, if an adverse event (AE) onset is on or after the first dose of trial intervention, the AE will be considered as a treatment-emergent adverse event (TEAE). Otherwise, the AE will be considered as a non-TEAE. Safety data will be presented separately for different study periods as defined in Table 5. In addition, the total number of participants with missed doses and reasons for missing (COVID-19 related or others) will be summarized by treatment group and overall.

Table 5 TEAEs for Different Study Periods

Study Period	Inclusion of TEAEs for Summary
Stage I (Safety Analysis Set)	Include AEs with an onset on or after the first dose of trial intervention in Stage I treatment period up to the time prior to the first dose of daxdilimab in Stage II treatment period ([REDACTED]) for participants who were dosed during the Stage II treatment period, and AEs with an onset on or after the first dose of trial intervention in Stage I treatment for participants not dosed in Stage II treatment.
Stage II (Stage II Analysis Set)	Include AEs with an onset on or after the first dose of daxdilimab in Stage II treatment period ([REDACTED]).

Table 5 TEAEs for Different Study Periods

Study Period	Inclusion of TEAEs for Summary
Any Daxdilimab Exposure (Any Daxdilimab Analysis Set)	Include AEs with onset on or after the first daxdilimab dose (either during Stage I or Stage II treatment period)

All AEs and TEAEs will be coded using the most recent version of MedDRA, and will be summarized by SOC and PT overall, by severity and by relationship to treatment. Participants having multiple AEs within a category (eg, overall, SOC, PT) will be counted once in that category. Specific AEs will be counted once for each participant for calculating rates, but all events will be presented in participant listings. In addition, for severity/relationship tables, if the same AE occurs multiple times within a particular participant, the highest severity/most related event within a category and level of causality will be reported.

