SAEs and TEAEs will be summarized descriptively by treatment group and overall. Percentages will be based on the number of treated participants in the safety set within a treatment group and overall. Tables will be sorted by descending frequency of SOC and by descending frequency of PT within an SOC. Specific AEs will be counted once for each participant for calculating rates, but all events will be presented in participant listings. Listings will be provided for all TEAEs and non-treatment-emergent AEs.

TESAEs will be summarized by serious adverse event (SAE) criteria as well.

The following definitions will be used for AEs:

- **Treatment-emergent adverse event (TEAE):** Any AE with an onset on or after the first dose of study intervention
- **Treatment-emergent SAE (TESAE):** A TEAE that is serious. The details are referenced in Section 8.3.1.3 of protocol

A table will show the number and percentage of participants with at least one event in any of the following categories overall as well as by SOC and PT:

- TEAE
- Treatment-emergent serious adverse event (TESAE)
- TEAE resulting in death
- CTCAE Grade 3 or higher TEAE
- TEAE leading to discontinuation of trial intervention
- Serious and/or grade 3 or higher TEAE
- Trial intervention related TEAE
- Trial intervention related TESAE

An AE of special interest (AESI) is an AE of scientific and medical interest specific to the understanding of the trial intervention and may require close monitoring and collection of additional information by the Investigator. AESIs for this protocol include:

- Hypersensitivity reaction, including anaphylaxis
- Severe viral infection/reactivation (CTCAE v5.0 Grade 3 or higher)
- Opportunistic infection as listed in protocol appendix 2
- Malignancy (except non-melanoma skin cancer)

Treatment emergent AESIs will be summarized by type of AESI as listed above as well as SOC and PT.

Anaphylaxis will be searched using the NIAID (Sampson et al. 2006). The hypersensitivity reactions will be defined using Standardized MedDRA Queries (SMQ): hypersensitivity (narrow). Severe viral infection will be searched using MedDRA HLGT of Viral infectious disorders. Viral reactivation will be searched using MedDRA HLT Hepatic viral infection. Malignancy will be searched using MedDRA SMQ Malignant tumors. All will be described in the Statistical Programming Plan (SPP).

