4.9.2.3 Prior and Concomitant Medications

Prior and concomitant medications and procedures will be summarized using the safety analysis sets accordingly. The details of prior and concomitant medications are described in Section 6.7 of the protocol.

Medications collected at Screening and during the trial will be coded using the current version of the World Health Organization Drug dictionary (WHO-DD). Number (%) of participants who received prior medications and concomitant medications will be summarized by treatment presented by WHO-DD Anatomical Therapeutic Chemical (ATC) category and PT. At each level of summarization, a participant is counted once if the participant reported one or more medications at that level. The summary of prior and concomitant medications during Stage I will be based on safety analysis set. The concomitant medications during Stage II will be summarized based on the second-year analysis set. The prior and concomitant medications are defined as below.

- Prior medications are defined as medications with a stop date occurring before the first trial intervention administration date.

- Concomitant medications during Stage I are defined as follows:
 - Medications with a start date before Week 64 trial intervention administration and stop date on or after the first trial intervention administration date for the participants entering the second-year treatment period.
 - Medications with stop date on or after the first trial intervention administration date for participants not entering the second-year treatment period.
- Concomitant medications for Stage II are defined as medications with a stop date on or after Week 64 daxdilimab administration date.

Rescue therapy for worsening LN may be administered at the discretion of Investigators as clinically indicated. Final rescue therapy will be reviewed and determined before unblinding at the end of Stage I.

Rescue therapy includes:

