4.15 Final Analysis

The final analysis will be conducted after all participants have completed the Week 112 Visit or discontinued early from the study.

By study design, the participants may undergo the different [REDACTED] based upon the renal response observed at Week 48 and Week 52. Thus, in the final analysis, the participants will be divided into two subgroups based on their PRR/CRR status at the Week 48 through Week 52:

- PRR/CRR Subgroup: Participants who achieved PRR or CRR at Week 48 and sustained through Week 52 will remain in their treatment groups. Statistical modeling can be used to examine the treatment effect between treatment groups over the Stage II of treatment (i.e., [REDACTED] mg [REDACTED] vs. placebo and [REDACTED] mg [REDACTED] vs. placebo), as applicable. All endpoints defined in primary, secondary and [REDACTED] will be analyzed. Some key endpoints examples are highlighted below.
- Non-PRR/CRR Subgroup: Participants who did not achieve PRR or CRR at either [REDACTED] will be administered daxdilimab [REDACTED] mg SC [REDACTED] through [REDACTED] (last dose administered at [REDACTED]). The final analysis for this subgroup will be descriptive only. No statistical modeling will be performed and no formal statistical comparison between treatment groups will be tested. All endpoints defined in primary, secondary and [REDACTED] except for all time-to-event endpoints, will be analyzed. Some key endpoints examples are highlighted below.

In the final analysis, all analyses planned for the primary analysis will be rerun with the Full Analysis Set.

For the non-PRR/CRR subgroup, the following analyses up to the Week 112 visit will be covered in the final analysis using Stage II Analysis Set:

- Proportion of participants achieving PRR or CRR or [REDACTED] in the Stage II
- Change from baseline in eGFR. In addition, change from re-baseline (Week 64) in eGFR will be explored descriptively
- Change from baseline in UPCR. In addition, change from re-baseline (Week 64) in UPCR will be explored descriptively

- Proportion of participants with prednisone-equivalent dose ≤ 2.5 mg/day for participants with baseline OCS > 2.5 mg/day until Week 92

■ [REDACTED]
■ [REDACTED]
■ [REDACTED]

For the PRR/CRR subgroup, the following analyses using the data up to the Week 112 visit will be covered in the final analysis using Stage II Analysis Set:

- Proportion of participants sustaining PRR or CRR or [REDACTED] in the Stage II

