- Time to loss PRR or CRR in the Stage II after achieving PRR/CRR at Week 48 and Week 52
- eGFR slope
- Change from baseline in UPCR
- Proportion of participants with prednisone-equivalent dose ≤ 2.5 mg/day for participants with baseline OCS > 2.5 mg/day until Week 104
- [REDACTED]
■ [REDACTED]

In the final safety analysis, the data up to the Week 112 visit (see Section 4.9) will be used.

Summary statistics will be computed and displayed by treatment group for the PRR/CRR subgroup or by treatment pathway ([REDACTED] mg \rightarrow [REDACTED] mg, [REDACTED] mg \rightarrow [REDACTED] mg, placebo \rightarrow [REDACTED] mg) for the non-PRR/CRR subgroup and by visit, where applicable. Descriptive statistics for continuous variables will minimally include the number of participants, mean of the observed values/change from baseline, SD, minimum, median, and maximum. For categorical variables, frequencies and percentages will be presented. For analyses involved with statistical modeling, the analysis methods are as follows (if applicable):

- Time to loss at least PRR status: Kaplan-Meier cumulative distribution curves will be generated for each treatment group. Participants will be censored at the earliest of their treatment discontinuation time, receipt of rescue therapy, study withdrawal or death or at Week 112 when the event of at least PRR cannot be sustained after Week 52. A corresponding summary table will present the number of participants at risk, the number of participants responding, and the number of participants censored at each postbaseline time point by treatment groups. The table will also present the median, along with the corresponding 2-sided 90% CI of time to response. Cox proportional hazards model will be explored (if applicable) with treatment group included in the model adjusting for eGFR and 24-hour UPCR values collected at Week 52. The hazard ratio with associated 2-sided 90% CIs and p-values will be presented
- For continuous and binary endpoint endpoints, similar analysis methods will be applied as described in Section 4.8.3.2 of the SAP
- [REDACTED]
■ [REDACTED]

A line plot of proportion of PRR, CRR, [REDACTED] over time will also be produced by randomized treatment group or treatment pathway within each of the subgroups. Boxplots of change of [REDACTED] will also be plotted by randomized treatment group or treatment pathway within each of the subgroups.

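### SAP Table 5 switches adverse events from Stage I to Stage II at the first Stage II dose of daxdilimab, a dose that placebo responders never receive

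*SAP*

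**What the plan says.** Table 5 in SAP 4.9.1 assigns treatment-emergent events to periods. For participants dosed in Stage II, the Stage I row runs from first dose "up to the time prior to the first dose of daxdilimab in Stage II treatment period". The Stage II row opens at that same daxdilimab dose. For everyone else, the Stage I row takes events with "onset on or after the first dose of trial intervention in Stage I treatment for participants not dosed in Stage II treatment" and states no end. Percentages are crude: "Percentages will be based on the number of treated participants in the safety set within a treatment group and overall".

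Other parts of the SAP define Stage II by any study drug:

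- Section 4.4.4: "The stage II analysis set includes all participants who received at least one dose of trial intervention during the Stage II treatment period".
- Table 4 in 4.1 describes Stage II, after a blacked-out time point, as "trial intervention administration and safety/efficacy assessments + safety follow-up".
- The text of 4.1 has Stage II beginning at a visit, summarised by reassigned regimen, and names a Placebo/Placebo group.

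Section 4.15 explains why that group exists: "Participants who achieved PRR or CRR at Week 48 and sustained through Week 52 will remain in their treatment groups". Section 4.9.2.3 refers to the Week 64 dose as trial intervention when it closes Stage I, and then as daxdilimab: "Concomitant medications for Stage II are defined as medications with a stop date on or after Week 64 daxdilimab administration date".

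**The concern.** A placebo responder is dosed in Stage II, but with placebo. The event that closes Stage I and opens Stage II in Table 5 therefore never happens for that participant. Two consequences follow from the words as they stand. Second-year events on placebo are added to the Stage I placebo column, while both daxdilimab columns stop at the Stage II dose. The Placebo/Placebo column in Stage II then has a denominator but no possible events.

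The incidences of TEAEs, serious TEAEs and AESIs are stated secondary endpoints. Viral infection and reactivation, and opportunistic infection, are named important potential risks in Protocol 2.2.1. Stage I is the only comparison with placebo across all treated participants, because the Stage II comparison in 4.15 is confined to responders. A longer window on placebo alone makes daxdilimab look safer in the table that matters most.

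**Working it through.** The plan gives no figure on the event window. The sample-size paragraph (SAP 2.3), which supplies 70 per arm and the 25% placebo rate used below, does reproduce: power for 25% v 45% at two-sided 0.10 is 0.804, and the smallest significant difference is 0.130, against the stated 80% and 13%.

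**1. Who is affected.**

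| Stage I arm | Week 48/52 response | Stage II drug | Does Table 5 close Stage I? |
|---|---|---|---|
| Daxdilimab | yes or no | daxdilimab | yes |
| Placebo | no | daxdilimab | yes |
| Placebo | yes | placebo | no |

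**2. When Stage II starts.** Table 5's week is blacked out. Sections 4.9.2.3 and 4.15 point to Week 64. As a check, doses at Weeks 0 and 2 (2), every 4 weeks from 4 to 52 (13), and at 64, 76, 88 and 100 (4) total 19, the number in the protocol synopsis. The extra placebo window is then 112 − 64 = 48 weeks, because 4.15 says: "In the final safety analysis, the data up to the Week 112 visit" will be used.

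**3. Size, with a true excess on daxdilimab.** Assumptions: 52-week risk 5% on placebo and 10% on daxdilimab, constant hazard h = −ln(1 − risk)/52, no stopping, and a share q of placebo participants staying on placebo. The documents give neither the risks nor q; 25% is the planning rate for complete response, used here only as a lower value.

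- Week 64 cut in both arms: placebo 1 − exp(−64h) = 6.12%, daxdilimab 12.16%, difference 6.04 points.
- Placebo to Week 112: 10.46%.
- Literal Stage I placebo risk = (1 − q) × 6.12 + q × 10.46, which is 7.20% at q = 0.25 and 8.29% at q = 0.50. The differences are 4.96 and 3.87 points.
- Primary analysis, with 12 extra weeks of data beyond Week 64: 5.77 and 5.49 points. With 24 extra weeks: 5.49 and 4.95.
- Stage II Placebo/Placebo: 0% shown, against 1 − exp(−48h) = 4.62%.

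**4. Size, with no true difference.** Assume 5 first events per 100 person-years in every arm, q = 0.40 and 52.18 weeks per year. Daxdilimab shows 5.9% and placebo 7.6%, a risk ratio of 0.78 where the truth is 1.00. For q from 0.25 to 0.55 and 2 to 20 events per 100 person-years, the ratio runs from 0.71 to 0.87.

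**5. Precision.** The 95% half-width at 70 per arm is 1.96 × √(0.05 × 0.95/70 + 0.10 × 0.90/70) = 8.7 points. The largest shift in step 3 is 6.04 − 3.87 = 2.17 points.

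**6. Participants not dosed in Stage II.** If follow-up ends at the later of Week 52 and last dose + 12 weeks, the time counted beyond last dose + 12 weeks is 52 − 12 − 12 = 28 weeks for a last dose at Week 12, 16 for Week 24, and none from Week 40 on. To see what this does over 52 weeks, use the step 3 risks, stopping at Week 24, and 10% to 25% of stoppers switching to an agent with a 20% to 30% annual risk. Risks are: completers 1 − exp(−52h); switchers 1 − exp(−24h − 28h_off); other stoppers 1 − exp(−36h − 16h_placebo). The on-treatment count stops switchers at Week 24 and other stoppers at Week 36.

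| Stopping, placebo/daxdilimab | Full-period difference | On-treatment difference |
|---|---|---|
| 25% / 25% | 4.5 to 4.6 | 4.6 |
| 20% / 15% | 4.5 to 4.7 | 4.8 to 4.9 |
| 30% / 15% or 40% / 20% | 3.9 to 4.6 | 5.0 |
| 15% / 30% or 20% / 40% | 4.5 to 5.0 | 3.9 to 4.3 |

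**The case against.** The best defence is that the intended rule can be recovered. Section 4.1 starts Stage II at a visit and names a Placebo/Placebo group, 4.4.4 and Table 4 speak of trial intervention, and 4.9.2.3 uses both terms for one Week 64 dose. The blacked-out bracket in Table 5 may name the week, and the Statistical Programming Plan, which is not available here, may settle it. An empty Placebo/Placebo column would look wrong to any programmer. Strictly, the literal text leaves the Stage I end undefined for these participants, and Week 112 is one reading. Most of this stands: it is probably a drafting slip. It does not rescue the wording, since a week number in the bracket would not remove the words that tie the cut to daxdilimab.

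A reader might go further and infer that Table 5 also leaves early stoppers with no end, so that off-drug and post-switch events contaminate Stage I. The documents do not support calling that an error. Protocol 4.1 and 7.1.1 follow early stoppers through Week 52 and for at least 12 weeks after the last dose, and the partly blacked-out synopsis takes the longer. Counting every event after first dose is a coherent choice. Step 6 shows little effect unless stopping is very unequal. The on-treatment percentage is no more reliable: it understates when daxdilimab stops more, and its agreement with the no-stopping 5.0 points in the third row comes from cutting placebo's window more often. One loose end remains: SAP 4.8.2.1, for the eGFR estimand, has those who discontinue evaluated until the end of study, which is longer than the protocol's Week 52.

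**Conclusion.** The point holds as a wording error of minor to moderate weight. As written, both rows of Table 5 depend on a dose that placebo responders never receive. If programmed literally, only placebo's Stage I window lengthens, a daxdilimab excess is diluted, and Placebo/Placebo shows no Stage II events. In the illustration, 6.0 points becomes 5.0 to 3.9 at Week 112 and 5.8 to 4.9 at the primary cut. This rests on assumed risks, a constant hazard, an assumed share of placebo responders and a Week 64 start.

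It would be too strong to infer that the trial's safety comparison is invalid. The shifts are well inside the 8.7-point half-width, SAP 4.9.1 plans no formal hypothesis for safety, and the intent can partly be read elsewhere in the SAP. The open-ended clause for participants not dosed in Stage II is a matter of preference.

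**What to change.** In both the Stage I and Stage II rows of Table 5, replace the first dose of daxdilimab with *first dose of study intervention (daxdilimab or placebo)*. Both rows must change; altering only Stage I would leave placebo responders' second-year events in neither table. Leave the Any Daxdilimab row alone, where daxdilimab is the right trigger. In 4.9.2.3, change the Week 64 daxdilimab date in the Stage II medication definition to the Week 64 study intervention date. The cost is a few words in the SAP, with no protocol change and no new data.

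Optional: for TEAEs and AESIs, give exposure-adjusted rates beside the crude percentages, with the person-time rule for early stoppers written out (for example, first dose to last dose + 12 weeks, counting only events in that span). SAP 4.6 already derives exposure, but its Stage I formula contains a blacked-out date. I would not end person-time at the first prohibited medication: the list in Protocol 6.7.2 includes vaccines, transfusions and steroids that count only beyond two weeks, so the date is unclear. The rates assume a roughly constant hazard and stopping unrelated to infection risk, so they belong beside the planned table and should not replace it.

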In this Phase 2 trial in participants with active, proliferative LN, daxdilimab will be compared to placebo in addition to SOC background therapy. In a Phase 2 study in a similar population of proliferative LN patients evaluating anifrolumab up to [REDACTED], a Type-1 IFNAR antagonist mAb, the dosage approved for the treatment of moderate to severe SLE [REDACTED] was no different from placebo in inducing renal responses whereas an intensified dosing regimen consisting of 3 months of induction with anifrolumab [REDACTED] demonstrated a trend towards a higher proportion of patients achieving renal response at 1 year. This difference may be explained by potential IFN overexpression in the kidneys and potential loss of anifrolumab concentration due to proteinuria. One of the main mechanism of actions of pDC depletion is through suppression of the overactivated Type-1 IFN system and prompt suppression of IFN activity in the kidney is thought to be key to achieving meaningful therapeutic responses. Given the overlapping mechanism of action and potential urinary loss of daxdilimab in patients with proteinuria, we propose to initiate treatment with daxdilimab [REDACTED] SC or placebo at baseline [REDACTED] to minimize the risk of undertreatment due to an insufficient dose or urinary loss of daxdilimab. Starting at Week 8, participants on daxdilimab will receive either daxdilimab [REDACTED] or daxdilimab [REDACTED] through [REDACTED]; at [REDACTED] all participants will be assigned to a [REDACTED] based upon the renal response observed at [REDACTED] and will either receive daxdilimab or placebo every [REDACTED] through [REDACTED] (last dose administered at [REDACTED]) in addition to SOC therapy.

A 52-week treatment duration is considered sufficient to demonstrate an effect on the primary and secondary outcome measures selected for this study. The second year of the trial will provide additional data to evaluate long-term safety as well as the [REDACTED]

[REDACTED] Current nonclinical safety data, the clinical study currently enrolling participants with SLE that will dose daxdilimab for [REDACTED], and belimumab's Phase 3 trial dosing through [REDACTED] support this treatment duration.

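### SAP Table 5 splits Stage I from Stage II adverse events at a daxdilimab dose that placebo responders never receive

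*SAP*

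**What the plan says.** SAP Section 4.9.1, Table 5, assigns treatment-emergent events to stages as follows.

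- **Stage I**, "for participants who were dosed during the Stage II treatment period": events from the first dose "up to the time prior to the first dose of daxdilimab in Stage II treatment period".
- **Stage I**, "for participants not dosed in Stage II treatment": all events from the first dose, with no end point.
- **Stage II** (Stage II Analysis Set): "Include AEs with an onset on or after the first dose of daxdilimab in Stage II treatment period".

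Other sections determine who receives what in Stage II.

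- SAP 4.15: "Participants who achieved PRR or CRR at Week 48 and sustained through Week 52 will remain in their treatment groups". SAP 4.1 accordingly lists a placebo/placebo reporting group.
- Protocol 4.3, on the same period: participants are assigned by renal response "and will either receive daxdilimab or placebo every" dosing interval (interval redacted).
- SAP 4.4.4: the Stage II Analysis Set is "all participants who received at least one dose of trial intervention during the Stage II treatment period".
- SAP Table 4 separates the two periods by administration of trial intervention, not of daxdilimab.
- SAP 4.9.2.3 ends Stage I concomitant medication at the Week 64 trial intervention, but for Stage II says: "Concomitant medications for Stage II are defined as medications with a stop date on or after Week 64 daxdilimab administration date".

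**The concern.** A boundary between study periods has to exist for every participant in the tables it divides. Here it is tied to an active-drug dose, and one pathway, placebo responders continuing on placebo, receives no active drug. They are dosed in Stage II, so the open-ended clause for undosed participants does not cover them, and the cut point given for dosed participants never arrives.

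Treatment-emergent events, serious events and events of special interest are secondary endpoints, and the tables report the percentage of participants with at least one event. A longer window in one arm raises that arm's percentage directly. The two stages are distorted in opposite directions. Stage I placebo is inflated, so daxdilimab looks safer. In Stage II, placebo/placebo shows no events over a non-zero denominator, so daxdilimab looks worse and the only concurrent placebo control is lost. The protocol gives long-term safety as one purpose of the second year, so the Stage II comparison matters.

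**Working it through.** The plan states no figure on this point, so the check is first logical and then illustrative.

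**Table 5 applied to each pathway**

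| Pathway | In Stage II Analysis Set | Stage II daxdilimab dose | Stage I closes | Stage II opens |
|---|---|---|---|---|
| Daxdilimab, continuing on daxdilimab | yes | yes | yes | yes |
| Placebo non-responder, moved to daxdilimab | yes | yes | yes | yes |
| Placebo responder, continuing on placebo | yes | **never** | **never** | **never** |

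**Inputs**

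- Start of Stage II dosing: Week 64. The visit is redacted in Tables 4 and 5; Week 64 is inferred from SAP 4.9.2.3 and from the re-baseline in 4.15.
- End of safety data: Week 112 (SAP 4.15).
- Placebo arm: 70 participants; planning response rate 25% (SAP 2.3). That rate is for complete response. The documents give no rate for partial or complete response combined, which is what decides who stays on placebo, so 35% and 50% are used as assumptions.
- Full follow-up is assumed.

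**Length of the Stage I window**

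Per placebo/placebo participant: 112 against 64 weeks; 112/64 = 1.75, or +75%.

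Mean over the placebo arm, with n continuing on placebo: [(70 − n) × 64 + n × 112] / 70. Person-weeks placed in the wrong stage: n × 48.

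| Continuing on placebo | n | Mean Stage I window | Excess | Misplaced person-weeks |
|---|---|---|---|---|
| 25% | 17.5 | 76.0 weeks | +18.75% | 840 |
| 35% | 24.5 | 80.8 weeks | +26.25% | 1,176 |
| 50% | 35 | 88.0 weeks | +37.5% | 1,680 |

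**Effect on reported incidence**

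Assume a constant hazard, equal in all arms, and let r64 be the risk at 64 weeks.

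- h = −ln(1 − r64)/64
- r112 = 1 − exp(−112h)
- Reported placebo Stage I risk = (1 − f) × r64 + f × r112, where f is the fraction continuing on placebo
- Spurious daxdilimab/placebo ratio = r64 / reported placebo risk
- Stage II placebo/placebo risk over 48 weeks = 1 − exp(−48h), reported as 0%

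For r64 = 10%: r112 = 16.8%. With f = 0.25, 0.75 × 10% + 0.25 × 16.8% = 11.7%. With f = 0.50, 0.50 × 10% + 0.50 × 16.8% = 13.4%.

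| r64 (assumed) | r112 | Reported placebo, f = 0.25 | Reported placebo, f = 0.50 | Ratio | Stage II risk shown as 0% |
|---|---|---|---|---|---|
| 10% | 16.8% | 11.7% | 13.4% | 0.85 to 0.75 | 7.6% |
| 30% | 46.4% | 34.1% | 38.2% | 0.88 to 0.79 | 23.5% |
| 70% | 87.8% | 74.5% | 78.9% | 0.94 to 0.89 | 59.5% |
| 90% | 98.2% | 92.1% | 94.1% | 0.98 to 0.96 | 82.2% |

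**Timing**

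The primary analysis uses all safety data up to its cut-off, after the last participant's Week 52 visit (SAP 3.2). Anyone enrolled more than 64 − 52 = 12 weeks before the last participant would by then be past Week 64. The documents give no accrual time, so the extent at that analysis is unknown.

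**The case against.** The strongest reply is that this is a slip that would be resolved in practice. In both Table 5 stage rows the words about the Stage II treatment period are followed by a redacted parenthesis, which may name a visit and so give a usable boundary for every arm. The rest of the SAP sets the boundary without reference to the drug: Table 4, the Stage II Analysis Set and the Stage I concomitant-medication rule all use trial intervention. The detailed specifications are in a separate programming plan, and a group with no events over 48 weeks would be noticed in table review. Safety carries no formal hypothesis, the efficacy analyses are untouched, and the participant listings and the Any Daxdilimab summary are unaffected. The distortion is also modest for common events: an earlier daxdilimab study cited in the protocol (Section 2.2.1) saw any treatment-emergent event in 72.7% of daxdilimab and 66.7% of placebo subjects.

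Much of this limits the size. The Stage I ratios are largest for the less common events, such as serious events and events of special interest, and approach 1 for the overall event table. It does not remove the fault. Whatever visit the parenthesis names, the stated rule is still a dose of daxdilimab. On the softest reading the cut point is undefined for placebo/placebo participants, which a programmer should not have to settle. That other sections use the right term shows the SAP contradicting itself, and the Stage II zero does not depend on the event rate.

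**Conclusion.** The concern holds. As written, Table 5 assigns all on-study events of placebo/placebo participants to Stage I and none to Stage II, in conflict with Table 4 and the Stage II Analysis Set. The Stage II line of SAP 4.9.2.3 has the same fault; its Stage I line does not. The affected group would be about 17 to 18 of 70 placebo participants at the planning rate, more once partial responders are counted and fewer after dropout before Week 64. For an event with 10% risk at 64 weeks, the spurious Stage I ratio is 0.85 to 0.75 and a Stage II risk of 7.6% is shown as 0%. These sizes rest on a Week 64 split, full follow-up to Week 112, a constant hazard equal across arms, and 25% to 50% of the placebo arm continuing on placebo. The logical fault rests on none of them. It should be corrected before the by-stage safety tables are programmed.

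**What to change.** In SAP Table 5, in both the Stage I and the Stage II rows, define the cut point as the first dose of trial intervention (daxdilimab or placebo) in the Stage II treatment period. In SAP 4.9.2.3, define Stage II concomitant medications by the Week 64 trial intervention administration date, matching the Stage I rule in the same list. Leave the Any Daxdilimab row of Table 5 unchanged, because a daxdilimab dose is the right starting point there. Every participant dosed in Stage II then has a Stage I window ending at that dose, and placebo/placebo events over the following 48 weeks appear in Stage II.

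The cost is three phrases in the SAP and the matching lines in the programming specifications. Nothing in trial conduct, data collection or the efficacy analyses changes.
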